MCM are defined as defects of prenatal origin that have either cosmetic or functional significance to the child's health, development, or survival. In this study, MCM ascertainment will be based on the presence of an ICD-10 code (or other database specific coding system [codes to be adapted to the coding systems used in each of the data sources]) in the database. These ICD-10 codes will be classified according to the EUROCAT (Description of the Congenital Anomaly Subgroups in EUROCAT Guide 1.5 classification scheme, as four of the five countries are in Europe. As a sensitivity analysis, all congenital malformations will be mapped to the Metropolitan Atlanta Congenital Defects Program (MACDP) USA-based classification system for MCM.

The MCM ascertainment period is defined as:

- for live births, from birth until 1 year of age
- for non-live births (spontaneous abortion and stillbirth) an ICD-10 code of MCM as the diagnosis at end of pregnancy
- for elective terminations, an ICD-10 code of an MCM as the reason for the termination at termination of pregnancy

The select pregnancy loss outcomes (composite of spontaneous abortion and stillbirth) will be defined as the presence of at least one of the following criteria:

- an ICD-10 code of spontaneous abortion (unintended loss of an intrauterine pregnancy which is less than 22 weeks of gestation for the European data sources; less than 20 weeks for the USA data sources)
- an ICD-10 code of stillbirth (unintended foetal death occurring at or after 22 weeks of gestation for the European data sources; at or after 20 weeks for the USA data sources)

Secondary outcomes

Minor congenital malformations (mCM)

mCM among live and non-live offspring are a structural anomaly or dysmorphic feature which does not impair viability or require intervention or treatment. mCM will be defined as a composite outcome. In this study, mCM ascertainment will be based on the presence of an ICD-10 code (or other database specific coding system [codes to be adapted to the coding systems used in each of the data sources]) in the database. These ICD-10 codes will be classified according to the EUROCAT (Description of the Congenital Anomaly Subgroups in EUROCAT Guide 1.5) classification scheme, as four of the five data countries are in Europe.

Adverse pregnancy outcomes

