9. RESEARCH METHODS

9.1 Study design

The study will be performed using a non-interventional longitudinal population-based retrospective cohort design. It will be conducted using secondary data derived from multiple databases in Denmark, Finland, France, Germany, and USA. The unit of analysis is individual pregnancies in women with moderate/severe SLE. Therefore, each woman may contribute multiple occurrences of pregnancies to the study.

There are two primary outcomes of interest: **composite of MCM** and **select pregnancy loss outcomes**. The ascertainment period for MCM is from the end of the pregnancy until one year of age, while the ascertainment period for select pregnancy loss outcomes is from LMP2 until end of pregnancy. The study design schemas for these outcomes are provided in Figure 1 (MCM) and Figure 2 (select pregnancy loss outcomes) below.

The secondary outcomes of interest are mCM, adverse pregnancy outcomes, and adverse birth outcomes. The outcome ascertainment periods for these secondary outcomes are from birth until one year of age (mCM), from LMP2 until end of pregnancy (adverse pregnancy outcomes) and at birth (adverse birth outcomes). The study design schemas are presented in Figure 1 (mCM), Figure 2 (adverse pregnancy outcomes) and Figure 3 (adverse birth outcomes).

The exploratory outcomes of interest are adverse outcomes related to infant growth. The ascertainment period for this outcome is from birth until 1 year of age. The study design schema is presented in Figure 4. In addition to this exploratory outcome, analysis for the select pregnancy loss outcome (composite of spontaneous abortion and stillbirth) by specific trimester of anifrolumab exposure (details as provided in Section 9.3.1), and the risk of MCM by target body organ system classification according EUROCAT (41) will be conducted.

For congenital malformation (CM), birth and infant outcomes, the population of study will be limited to offspring for whom mother-offspring record linkage is available within each data source. However, for pregnancies that end in a spontaneous abortion, an elective termination of pregnancy or stillbirth where there is a diagnosis of MCM, mother-offspring linkage will not be required.

The exposure of interest is *in utero* exposure to anifrolumab (see Section 9.3.1) and/or *in utero* exposure to SLE SOC between last menstrual period + 2 weeks (LMP2) (derived from last menstrual period or, if missing, gestational age) and:

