- g. Exposure to SLE SOC will be assessed in the exposed and comparator groups at LMP2 with a look-back period of 5-half-lives of relevant drug. Exposure to anifrolumab will be assessed from LMP2 until end of the first trimester of pregnancy for MCM outcome and anytime during the pregnancy for mCM outcome with a maximum look-back period of 16-weeks (time for anifrolumab concentration to fall below the LLOQ for 95% of patients) prior to LMP2
- h. Comorbidities and covariates measured during pregnancy may include maternal smoking, alcohol and substance abuse, gestational diabetes
- i. First of the following: diagnosis of CM, death, emigration, end of study period (reaching the age of 1 year), and administrative data cut off
- j. Covariates measured at index date may include maternal socioeconomic status (SES), age at LMP2

[figure not shown]

Figure 2: Overview of the study design, for adverse pregnancy outcomes

- a. Diagnosis of SLE before pregnancy
- b. Women with a continuous enrolment in the database for ≥ 12 months prior to conception (defined as LMP2)

- c. Singleton pregnancy, mother-offspring linkage. Mother-offspring linkage will be required for ectopic pregnancy, spontaneous abortion, elective termination, stillbirth, infections requiring hospitalisation, caesarean section
- d. Women with a history of CM or chromosomal abnormalities
- e. Pregnancy associated with in vitro fertilisation (IVF), date of conception cannot be established
- f. Comorbidities and covariates measured prior to index date may include maternal diabetes, maternal pre-pregnancy BMI, obstetric history
- g. Exposure to SLE SOC will be assessed in the exposed and comparator groups at LMP2 with a look-back period of 5-half-lives of relevant drug. Exposure to anifrolumab will be assessed from LMP2 until end of pregnancy with a maximum look-back period of 16-weeks (time for anifrolumab concentration to fall below the LLOQ for 95% of patients) prior to LMP2
- h. Comorbidities and covariates measured during pregnancy may include maternal smoking, alcohol and substance abuse, gestational diabetes

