Secondary objective 5c-d, 6 & 7;	Describe and estimate the risk and relative risk of mCM. Describe cohort demographic and clinical characteristics. Among live and non-live offspring	Exposed study population	mCM_exp	
INCLUSION:
 
 • mCM: Pregnancies exposed to anifrolumab anytime during pregnancy (+16 weeks prior to LMP2) • All pregnancies ending in spontaneous abortion, elective termination of pregnancy and stillbirth, regardless of linkage mother-offspring within the study period • Pregnancies with linkage mother-offspring within the study time period 
EXCLUSION:
 
 • Adopted children (where available)
Secondary objective 5c-d, 6 & 7	Describe and estimate risk of and relative risk of mCM. Describe cohort demographic and clinical characteristics. Among live and non-live offspring	Unexposed study population	mCM_unexp	
INCLUSION:
 
 • All pregnancies ending in spontaneous abortion, elective termination of pregnancy and stillbirth, regardless of linkage mother-offspring within the study period • Pregnancies with linkage mother-offspring within the study time period 
EXCLUSION:
 
 • Pregnancies exposed at any time to anifrolumab (+16 weeks prior to LMP2) (see Section 9.3.1) • Adopted children (where available)
Primary and Secondary cohort pregnancy (pregnancy_exp+ pregnancy_unexp)				
Primary objective 3 & 4	Describe and estimate risk of select pregnancy loss outcomes (composite of spontaneous abortion and stillbirth), adverse	Exposed study population	pregnancy_exp	
INCLUSION:
 
 • Pregnancies exposed at any time to anifrolumab (+16 weeks prior to LMP2)

Objective	Main features	Input Cohort/ Population	Sub-cohort Abbreviation	Additional criteria to be applied to the input Cohort/ Population

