The MBR consists of a main table with index pregnancy (one line for each infant in the same pregnancy) as the key identifier and information on the identity on both parents by CPR number, diagnosis (ICD-10 codes) and possible complications, potential risk factors and number of prenatal visits. Any congenital abnormalities are retrospectively added to the table if identified within the first year of life. All subsequent health events reported by diagnoses and surgical interventions can be found in the NPR. All deaths of mother or infant within the first 365 days after delivery are registered including the age in days when the infant died.

- **The Danish Cause of Death Register (CDR)**

The Danish Cause of Death Register (CDR) contains information on date and cause of death. The information from the death certificate, including place of death, information about any autopsy, and municipality of residence is transferred to the CDR. Date of death is available from 1970 onwards. The register is updated once a year after end of December with a lag of approximately 13 months.

- **The Socio-economic registers at Statistics Denmark**

The Socio-economic registers cover a wide range of information on residents in Denmark. These include annual income by individual or family, highest achieved education, occupation, proportion of time outside employment due to sick leave etc., and information on individuals receiving different types of disability aid. Socio-economic registers at Statistics Denmark are updated annually, typically after end of December.

Study-specific data availability

The estimated annual number of pregnancies in women with SLE eligible for the MCM analysis and the select pregnancy loss outcomes analysis is 12 and 16, respectively (see Section 9.5.1 and Table 9).

Mother-offspring linkage is available since 1973, and all live births and stillbirths after 22 weeks of gestational age can be linked. This linkage is achieved using a deterministic approach.

Anifrolumab received marketing authorisation in Denmark in February 2022 and had a market launch in March 2022 (Table 4). It is provided to patients without any additional out of pocket costs. In Denmark, it is assumed that anifrolumab would be captured in SMR as it is administered at the hospital and administration of belimumab was captured in the registry.

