The estimated annual number of pregnancies in women with SLE eligible for the MCM analysis and the select pregnancy loss outcomes analysis is 10 and 12, respectively (see Section 9.5.1 and Table 9).

Mother-offspring linkage is available since 1987, and all live births and stillbirths after 22 weeks of gestational age or with a birth weight over 500g can be linked. This linkage is achieved using a deterministic approach.

Anifrolumab received marketing authorisation in Finland in February 2022 but has not yet had a market launch. Finland's wellbeing counties have their own or a combined procurement agreement for hospital administered drugs. In this procurement agreement, it is decided which specific products will be used for that specific procurement period. If the drug (e.g., anifrolumab) is listed in the procurement agreement, it will be provided to patients without any additional out of pocket costs.

In Finland, information on drugs prescribed in hospital or in other institutional care and drugs administered in hospital or in other institutional care are available with possible unavailability in case of small patient counts (<5). In Finland, prescriptions and dispensing of oral and subcutaneous (SC) biologics are available from prescription registers, hospital administered medication, including anifrolumab, are available from EMRs. ATC codes will allow the distinction between biologics.

In Finland, all study outcomes of interest are available or partially available (Table 16), as well as maternal characteristics, other baseline characteristics and covariates (Table 17).

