Assuming 50% of SLE pregnancies occur in women with moderate-to-severe disease, the expected number of SLE pregnancies in women with moderate-to-severe disease was obtained by multiplying the number of reported or estimated pregnancies in SLE women (step 2) by 0.5. This resulted in an estimate for the annual number of pregnancies in women with moderate-to-severe SLE to be 224 (Carelon Research), 222 (DAPI), 20 (Denmark), 16 (Finland), 279 (France) and 25 (RHEKISS). Furthermore, 20% of pregnancies in women with moderate-to-severe SLE are expected to be excluded from analysis due to exposure to SLE SOC and non-SLE SOC confirmed teratogenic drugs before conception, with a time period of 5-half-lives of relevant drug (see [Table 20](#)), or during the pregnancy. Thus, the estimated annual number of pregnancies in women with moderate-to-severe SLE eligible for analysis were 179 (Carelon Research), 178 (DAPI), 16 (Denmark), 12 (Finland), 223 (France) and 13 (RHEKISS) ([Table 9](#)).

In Denmark, Finland, France and RHEKISS data sources, all live births can be linked to a pregnancy. However, in USA data sources (Carelon Research and DAPI) not all live births can be linked to the mother: 73% and 85% of the pregnancies resulting in a live birth can be linked to the offspring in Carelon Research and DAPI, respectively. Thus, the MCM analysis can only be conducted in USA data sources (Carelon Research and DAPI) using the pregnancies resulting in live birth that can be linked to the mother or resulting in a recorded pregnancy loss or non-live birth. In other data sources, all pregnancies in women with moderate-to-severe SLE are eligible for both the MCM and the select pregnancy loss outcomes analysis. The estimated annual number of pregnancies in women with moderate-to-severe SLE that are eligible for MCM analysis were 112 (Carelon Research), 125 (DAPI), 12 (Denmark), 10 (Finland), 178 (France) and 10 (RHEKISS) ([Table 9](#)).

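### Figure 2 note c requires mother-offspring linkage for the adverse pregnancy outcomes, contradicting Section 9.1, Table 3, Table 5 and the study-size section; a 'not' was probably dropped

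*Protocol*

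**What the plan says.** Section 9.1 names Figure 2 as the schema for select pregnancy loss (spontaneous abortion plus stillbirth) and for the other adverse pregnancy outcomes. Its note c opens by listing singleton pregnancy and mother-offspring linkage as conditions, then adds: "Mother-offspring linkage will be required for ectopic pregnancy, spontaneous abortion, elective termination, stillbirth, infections requiring hospitalisation, caesarean section".

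Elsewhere the protocol reads differently:

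- **Section 9.1, body text (and Section 4):** "For congenital malformation (CM), birth and infant outcomes, the population of study will be limited to offspring for whom mother-offspring record linkage is available". Adverse pregnancy outcomes are not in that list.
- **Table 3:** the population for select pregnancy loss and for every adverse pregnancy outcome is all pregnancies, and offspring follow-up is not applicable.
- **Table 5 (Section 9.2.2):** the inclusion rule for the exposed pregnancy cohort is "Pregnancies exposed at any time to anifrolumab (+16 weeks prior to LMP2"), with a separate line on ectopic pregnancies. Linkage is not mentioned for either pregnancy sub-cohort. It is listed for the MCM, mCM, birth and infant cohorts.
- **Section 9.5.1.2:** "the MCM analysis can only be conducted in USA data sources (Carelon Research and DAPI) using the pregnancies resulting in live birth" (linked ones only), plus recorded losses and non-live births. The select pregnancy loss counts carry no such reduction. For the non-US sources, "all pregnancies in women with moderate-to-severe SLE are eligible for both the MCM and the select pregnancy loss outcomes analysis".
- **Figure 1 note c:** for malformation outcomes, linkage is waived for spontaneous abortion, stillbirth and ectopic pregnancy where the recorded diagnosis or reason is MCM.

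**The concern.** Note c is the only place that gives an explicit linkage rule for the adverse pregnancy outcomes. Table 5 is silent on linkage for this cohort rather than waiving it, so a programmer could add the note's condition to Table 5 without seeing a conflict. Section 9.6 has each data holder identify its own study population, and some holders analyse their own data, so sources could also diverge.

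The rule does not fit the data. Spontaneous abortion is defined as "unintended loss of an intrauterine pregnancy which is less than 22 weeks of gestation for the European data sources" and before 20 weeks in the USA. The linkage descriptions in Section 9.4.1 do not reach such pregnancies, except in RHEKISS. Applied literally, the note would remove the larger component of a primary composite while linked live births stayed in the denominator. Section 9.5.1.1 says the composite was chosen to evaluate embryo-foetal loss, so what remained would be close to a stillbirth-only analysis.

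**Working it through.** **1. What can be linked (Section 9.4.1)**

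| Source | Linkage described |
|---|---|
| Denmark | "all live births and stillbirths after 22 weeks of gestational age can be linked" |
| Finland | "all live births and stillbirths after 22 weeks of gestational age or with a birth weight over 500g can be linked" |
| France | live births and stillbirths, no threshold stated |
| Carelon | about 73% of live births |
| DAPI | 85% of live births; some non-matches are attributed to pregnancies without a delivery |
| RHEKISS | linkage inherent in data collection |

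That spontaneous abortions cannot be linked is an inference from these descriptions; the protocol does not say so outright. RHEKISS would lose none, but it is not among the sources in the 2032 meta-analysis (Table 13).

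**2. Reproducing the plan's figures without a linkage restriction**

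Inputs (Section 9.5): composite prevalence p = 0.20, margin RR 2.5, true RR 1, one-sided alpha 2.5%, power 80%, k = 2 or 3 comparators per exposed pregnancy. With the Poisson standard error of the log RR,

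n exposed = (1 + 1/k)/p × ((1.960 + 0.842)/ln 2.5)²

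ln 2.5 = 0.916, so the squared term is about 9.35.

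- k = 2: 7.5 × 9.35 = 70.1, rounded up to 71 (plan: 72).
- k = 3: 6.667 × 9.35 = 62.3, rounded up to 63 (plan: 61).

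Simulating the Section 9.5.1.3 method (source-level log RRs, fixed-effect inverse-variance pooling) gives 81.7% power at 72 exposed and 79.0% at 61. With 163 + 162 + 11 + 145 = 481 exposed in the four sources pooled at 10% uptake, power exceeds 99%. The plan's figures stand.

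**3. Events lost if note c were applied literally**

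Section 9.5.1.1 cites 16% (12.1% to 19.9%) for spontaneous abortion and 1.8% to 3.7% for stillbirth.

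- Spontaneous abortion share of the composite: 16/(16 + 3.7) = 81%; 16/(16 + 1.8) = 90%. Over the full cited ranges it is 77% to 92%.
- Against the planned 20%, keeping stillbirths only: 1 − 3.7/20 = 81.5% lost; 1 − 1.8/20 = 91% lost.
- Exposed events at 10% uptake: 481 × 0.20 = 96.2 planned; 481 × 0.018 = 8.7 to 481 × 0.037 = 17.8 kept.
- If US stillbirths were also unlinkable, Denmark and France remain: 156 × 0.018 = 2.8 to 156 × 0.037 = 5.8 kept.

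**4. Illustrative power under the literal note**

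Same simulation at 1:2. Assumptions: 80% of pregnancies end in live birth, live births are linked at the quoted rates (100% outside the USA), all stillbirths are kept, and sources with no event in either arm drop out.

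| Uptake | Stillbirth 1.8% | Stillbirth 3.7% |
|---|---|---|
| 10% | about 44% | about 88% |
| 5% | about 8% | about 46% |

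The 5% row includes five Danish pregnancies that Table 13 leaves out at that uptake; omitting them moves power by no more than about one percentage point. The plan states above 99% in every scenario.

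**The case against.** The strongest reply is that the operative text is already right. Section 9.6 tells data holders to identify the population from Section 9.2, and Figure 2 sits in Section 9.1 as an overview. Table 5, within Section 9.2.2, has no linkage criterion for this cohort. Objective 3 divides by the total number of pregnancies. One figure note stands against all of this, and Figure 1's wording suggests a slip. This reply stands as far as likelihood goes: a programmer who follows Section 9.6 would not apply linkage here. It does not make the note correct, because the note is an explicit eligibility statement for a primary outcome and says the reverse of what is meant.

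A reader might infer more than the documents support:

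- **That the study will lose its second primary outcome, or that linkage is a deliberate design choice.** The loss arises only if note c is followed over Tables 3 and 5, and nothing else in the protocol suggests that it was intended.
- **That the sample size or power is wrong.** Section 9.5 assumes no linkage restriction for this outcome, and its figures reproduce on that basis.
- **That every spontaneous abortion would go.** RHEKISS linkage is inherent.
- **That US stillbirths would certainly go.** The Carelon and DAPI sections give a linked share of live births and do not describe stillbirth linkage either way.
- **That the loss of elective terminations affects the primary outcome.** They belong to the secondary foetal-loss composite.

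**Conclusion.** This is an internal contradiction, and note c is the text that is wrong. It reverses the linkage rule for the second primary outcome and for all the adverse pregnancy outcomes, so it should be corrected before the first data extraction (planned for 31 May 2025).

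If the note were followed literally, 81.5% to 91% of planned select pregnancy loss events would be lost. This rests on the protocol's 20% composite and 1.8% to 3.7% stillbirth prevalences, and on the inference that losses below the stillbirth threshold cannot be linked outside RHEKISS. Power would no longer exceed 99%. The simulated values are illustrative and depend on stillbirths remaining linkable in all pooled sources, which is favourable for the USA. On the reading that the rest of the protocol supports, no events are lost, and 72/61 and the stated power are unchanged.

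**What to change.** In Figure 2 note c, keep the singleton condition, delete the opening mother-offspring linkage condition, and state that linkage will not be required for ectopic pregnancy, spontaneous abortion, elective termination, stillbirth, infections requiring hospitalisation or emergency caesarean section. That aligns the note with Table 3, Table 5 and the body of Section 9.1.

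Adding the words 'regardless of linkage' to the two pregnancy cohort rows of Table 5 is optional. It would replace silence with an explicit rule, but the table is already correct.

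The cost is one corrected note. Section 9.5 needs no change, and no further data are required.

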9.2 Setting

A total of 6 large longitudinal patient-level data sources have been selected for this study, representing 5 countries: Denmark, Finland, France, Germany, and USA.

The included data sources are:

- Danish national health and socioeconomic registries (Denmark)
- Finnish national health and socioeconomic registries (Finland)
- National Health Data System (SNDS) (France)
- Rheuma-Kindwunsch und Schwangerschaft (RHEKISS) (Germany)
- Carelon Research (formerly known as Health Core Integrated Research Database - HIRD) (USA)
- Optum DAPI (USA)

